### 4.4.2 Data Collection and Follow-up for Withdrawn Subjects

If a Participant withdraws from the study, no additional attempts will be made to contact the Participant.

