## 4.4 Early Withdrawal of Subjects

### 4.4.1 When and How to Withdraw Subjects

Patients are free to withdraw at any time and for whatever reason. No data will be collected for withdrawn subjects and withdrawn subjects may be replaced within the accrual period. There will be no follow-up for withdrawn subjects. Pre-specified reasons for discontinuing include, but are not limited to, the following:

- Patient Request: Patient decided that he/she did not want to continue (for any reason)
- Adverse Event: Patient experienced a related or unrelated event that would interfere with the study objectives/evaluation
- Lost to Follow-up: Patient did not come in for a visit and could not be reached by phone
- Treatment Failure: If in the Principal Investigator and/or Investigators' judgment, the patient's condition required another form of treatment
- Mechlorethamine sensitization: Patient develops contact dermatitis to Valchlor that cannot be managed with low potency topical corticosteroids
- Inclusion/Exclusion Discrepancy/Violation: Patient should not have been enrolled
- Noncompliance: Patient is not complying with the protocol requirements (i.e. visit schedule, dosing, regimen, etc.); a patient is to be withdrawn if he/she misses two consecutive visits
- Other: Any other reason

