#### Adverse Event

An AE is defined as any untoward medical occurrence in a patient administered a pharmaceutical product and which does not necessarily have a causal relationship with the treatment. An AE can therefore be any unfavorable and unintended sign (including an abnormal lab finding), symptom or disease temporally associated with the use of a medicinal product, whether or not related to the medicinal product.

Each AE must be assessed by the investigator as to whether or not there is a reasonable possibility of causal relationship to Valchlor, and documented as either related or unrelated. The determination of the likelihood that Valchlor caused the AE must be provided by an investigator who is a qualified physician. .

Initial screening for AE will include non-directed questioning of the patient at each follow-up visit during the study period along with the directed questioning and examination regarding:

- Signs and symptoms of idiosyncratic allergic contact dermatitis

Patients will be instructed to stop using Valchlor and to contact the study coordinator if swelling and blistering occurs as this may represent early signs of allergic contact dermatitis. The primary investigator will then evaluate the patient and if the signs and symptoms are

compatible with allergic contact dermatitis, the patient will be offered treatment using a medium-potency topical corticosteroid to involved areas in the AM, with resumption of Valchlor application in the PM. Patients with persistent allergic contact dermatitis reactions unable to be managed as outlined above will exit the study.

- Unintentional mucosal and/ocular exposure

Patients will be warned not to apply Valchlor near eyes, mouth, or nose as it can cause pain, redness, swelling, burning, sensitivity to light, blurred vision, and blindness or permanent eye injury. If accidental Valchlor exposure to nose, mouth or eyes occurs, patients will be instructed to rinse affected areas with large amounts of water for 15 minutes and to contact the study coordinator. The primary investigator will then contact the patient to review application site instructions and schedule a follow-up evaluation if the patient reports persistent symptoms or erythema.

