### **Adverse Event Reporting Period**

For this study, the study treatment follow-up period is defined as the last scheduled visit.

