**Post-study Adverse Event**

All unresolved adverse events should be followed by the sponsor-investigator until the events are resolved, the subject is lost to follow-up, or the adverse event is otherwise explained. At the last scheduled visit, the sponsor-investigator should instruct each subject to report, to the sponsor-investigator, any subsequent event(s) that the subject, or the subject's personal physician, believes might reasonably be related to participation in this study.

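### Section 4.4 rules out data, follow-up and contact after withdrawal with no safety exception, while 8.1 and 8.2 want open adverse events followed, and nothing says which governs

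*Combined protocol and SAP*

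**What the plan says.** **On withdrawal.** Section 4.4.1 states: "No data will be collected for withdrawn subjects and withdrawn subjects may be replaced within the accrual period". It then adds: "There will be no follow-up for withdrawn subjects". Section 4.4.2 extends this to contact: "If a Participant withdraws from the study, no additional attempts will be made to contact the Participant". None of the three sentences carries a safety exception.

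**On why subjects leave.** Two of the reasons listed in 4.4.1 are adverse events in themselves. One is the general adverse event reason: "Patient experienced a related or unrelated event that would interfere with the study objectives/evaluation". The other is sensitization: "Patient develops contact dermatitis to Valchlor that cannot be managed with low potency topical corticosteroids". Section 8.1 (Adverse Event) has a matching rule: "Patients with persistent allergic contact dermatitis reactions unable to be managed as outlined above will exit the study".

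**On following adverse events.** Section 8.1 (Post-study Adverse Event) states: "All unresolved adverse events should be followed by the sponsor-investigator until the events are resolved, the subject is lost to follow-up", or until there is some other explanation for the event. Section 8.2 says each event should be followed until it resolves, stabilizes, or is judged not to be probably caused by study treatment or participation. It uses *must* for serious events still continuing when the study period ends. Neither section exempts withdrawn subjects.

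**On the reporting period.** Section 8.1 (Adverse Event Reporting Period) reads: "For this study, the study treatment follow-up period is defined as the last scheduled visit". It does not mention withdrawal.

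**The concern.** The protocol gives staff two instructions for the same patient. Someone who is withdrawn because a reaction to the gel cannot be controlled probably still has that reaction on the day of exit. Section 4.4 then tells staff to stop, and section 8 tells them to continue.

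If staff follow 4.4, nobody actively obtains the eventual outcome or the resolution date of the event. Both are items the protocol itself asks for: the adverse event documentation listed in 8.3.1 includes how the event resolved and when. Section 1.6 also gives, as a reason the dermatitis risk is minimized, that the reaction clears once Valchlor is stopped. The patients who leave because of dermatitis are the direct test of that statement, and under 4.4 the protocol would not look at them after they stop for good.

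**Working it through.** No figure is involved and no formula applies. The check sets the sections side by side and asks whether any other section resolves the difference.

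| Question | Section 4.4 | Section 8 |
|---|---|---|
| Who is covered? | Withdrawn subjects; the reasons listed include adverse event and sensitization | All unresolved events (8.1); each event (8.2) |
| What happens after exit? | No data, no follow-up, no contact | Follow until resolved, stable or explained |
| How strong is the wording? | Flat prohibition | *Should* in general; *must* for serious events ongoing when the study period ends |
| Is there an exception for the other rule? | None | None |

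**Step 1: do the rules meet in the same patient?** Yes. The dermatitis rules in 4.4.1 and 8.1 remove a patient because the reaction is not controlled, so the event is likely to be open at exit.

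**Step 2: does the loss-to-follow-up limit in 8.1 cover these patients?** No. Section 4.4.1 lists loss to follow-up as a separate reason and describes it as missing a visit and being unreachable by phone. A patient who exits for dermatitis and can be reached does not fit that description.

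**Step 3: does the reporting period settle it?** No. It refers to the last scheduled visit and is silent on early exit.

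**Step 4: does self-reporting fill the gap?** Only in part. Under 8.1, subjects are told at the last scheduled visit to report later events, and a withdrawn patient may never reach that visit.

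**Step 5: is there an exception elsewhere?** Section 9.1 provides for seeking permission to collect vital status from subjects who revoke authorization. Contact after departure is therefore not ruled out everywhere, but nothing extends this to open adverse events.

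**Step 6: what differs between the two readings?** Under 4.4, the outcome after exit is actively sought in 0 of the patients withdrawn for an adverse event or sensitization, however many there are. Under section 8, it is sought in each whose event is not yet resolved, stabilized or explained at exit. The documents give no basis for estimating that number or the time from exit to resolution.

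**The case against.** The strongest reply is that section 8 is the specific safety rule and section 4.4 a general rule about taking part in the trial. Two further sections support this. Section 8.3 has the sponsor-investigator decide what follow-up an identified event needs. Section 8.3.1 asks for resolution details, including whether the event cleared after treatment stopped. This is a reasonable reading, but neither section states a precedence, and 4.4.2 is just as specific to its own situation, as its heading names follow-up of withdrawn subjects. The resolution fields in 8.3.1 in fact show what would be left incomplete.

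A second reply is that 4.4.2 concerns participants who choose to leave, so that the no-contact rule respects their choice. The wording of 4.4.2 allows this. However, its heading covers withdrawn subjects generally, and 4.4.1 bars follow-up for withdrawn subjects in a list that includes removal for an adverse event or sensitization.

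A third reply is that 8.1 already has a patient with swelling or blistering stop the gel, call the coordinator and be evaluated before any exit, so some response to stopping can be seen. That is true as far as it goes. For a reaction judged to be allergic contact dermatitis, the next step is a topical steroid with Valchlor resumed, so this evaluation does not show the outcome after final discontinuation.

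Several limits do stand:
- The *must* sentence in 8.2 refers to the end of the study period, not to withdrawal. The firm overlap is with the *should* sentences.
- The form can still show the event as unresolved at exit, so what is lost is the later outcome and not the event record.
- For a non-serious event already stable at exit, 8.2 may ask for nothing more.
- The dermatitis statement in 1.6 is background on risk and is not an endpoint.

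**Conclusion.** The concern holds and should be fixed. Read as written, 4.4 leaves drug-related events without follow-up in patients removed because of them, section 8 says the opposite, and no section decides between them.

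The consequence is confined to the later outcome and resolution date of events open at exit, and it arises only if staff treat 4.4 as overriding section 8. Dermatitis incidence, the stopping-rule count in 8.5, the primary safety endpoint in 3.6 and the efficacy analysis need not change. The conclusion rests on the text alone and on no assumed rate of withdrawal or dermatitis.

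**What to change.** Add one exception to 4.4.1 and 4.4.2 and leave their other rules as they are. Suggested wording:

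*Any adverse event open at withdrawal will be followed for outcome as in 8.1 and 8.2, by phone or clinic contact, unless the participant refuses contact.*

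This gives staff one instruction, lets the resolution items in 8.3.1 be pursued for patients who exit with an open event, and keeps the participant's right to decline. The cost is a short amendment and a few extra phone or clinic contacts by existing staff at a single site. Some participants who have left may be contacted again about an open event.

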## 5 Study Drug

### 5.1 Description

VALCHLOR is a topical product that contains mechlorethamine HCl, an alkylating drug. Mechlorethamine HCl is a white to off white solid that is very soluble in water and methanol, partially soluble in acetone, and generally not soluble in organic solvents.

Mechlorethamine HCl is designated chemically as 2-chloro-*N*-(2-chloroethyl)-*N*-methylethanamine hydrochloride. The molecular weight is 192.52 and the melting point is 108-111°C. The empirical formula is C5H11Cl2N•HCl, and the structural formula is: CH3N(CH2CH2Cl)2•HCl.

Each tube of VALCHLOR contains 60g of a gel containing 0.016% w/w of mechlorethamine (equivalent to 0.02% mechlorethamine HCl) in a base of the following inactive ingredients: diethylene glycol monoethyl ether, propylene glycol, isopropyl alcohol, glycerin, lactic acid, hydroxypropylcellulose, sodium chloride, menthol, edetate disodium, butylated hydroxytoluene.

Systemic exposure was undetectable after topical administration of VALCHLOR to patients. Blood samples were analyzed from 16 and 15 patients following treatment with VALCHLOR (mechlorethamine gel 0.016%) and an identical formulation consisting of mechlorethamine 0.032% w/w, respectively. For patients who received mechlorethamine 0.016%, samples were collected to measure mechlorethamine concentrations prior to dosing, on day 1, and at the first month visit. Following the topical administration of mechlorethamine 0.016%, there were no detectable plasma mechlorethamine concentrations observed in any of the patients. Patients who received mechlorethamine 0.032% had no measurable concentrations of mechlorethamine or half-mustard after 2, 4, or 6 months of treatment.

## **5.2 Treatment Regimen**

All study participants will apply Valchlor 0.016% gel to involved areas at night, beginning with three times a week, (Mondays, Wednesdays and Fridays) and increasing to daily application after one month, if well tolerated, for a total of 6 months. Patients will be instructed to first part the hair away from involved area as needed, limit application to areas with alopecia and erythema, apply 30 minutes after showering or washing, and allow treated areas to dry for 5 to 10 minutes before covering with clothing or going to bed. Participants will be instructed to wash their hands with soap and water after applying Valchlor. Caregivers who assist in application will be instructed to wear disposable nitrile gloves when applying Valchlor and dispose with the household trash. Patients will be instructed to store Valchlor in the refrigerator away from foods at 36-46 degrees F and apply within 30 minutes after removing from refrigeration.

## **5.3 Method for Assigning Subjects to Treatment Groups**

This is an open-label pilot investigation and all study participants are assigned to active treatment with a topically applied study drug. There is no placebo arm in this study.

## **5.4 Preparation and Administration of Study Drug**

The study drug will be stored and dispensed to patients at each study visit from the Mayo Clinic Florida Research Pharmacy.

## **5.5 Subject Compliance Monitoring**

Study participants will be dispensed one 60 gram tube at the qualifying baseline exam, 2 tubes at week 4 following phone visit, and 3 tubes at the week 12 follow-up visit. They will be instructed to use one tube per 30 days and be will instructed to bring these tubes for all follow-up visits. Weights of each tube after 30 days of use will be recorded.

## **5.6 Prior and Concomitant Therapy**

Eligible participants using high-potency topical corticosteroids, intralesional corticosteroids, or oral hydroxychloroquine may enroll but will be required to discontinue use during the 6 month study duration.

Mild irritant reactions at site application may be treated with class IV topical corticosteroids in a gel vehicle the morning following nightly application on an as needed basis.

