### 1.1 Background

Lichen Planopilaris (LPP) is a form of lymphocyte mediated scarring alopecia. It is a chronic condition that predominates in women between the ages of 45-70. Patients present with discrete patches of hair loss with characteristic perifollicular erythema and scale [1]. Diffuse or localized scalp involvement may be seen. Disease progression results in irreversible hair loss and has been associated with significant impact on quality of life, depression, and anxiety [2]. Successful treatment of LPP requires clearance of the lymphocytic inflammation early in the disease course to prevent irreversible follicular destruction and permanent hair loss.

Conventional topical (e.g. corticosteroids) and systemic immunosuppressives (e.g. mycophenolate mofetil) used in the treatment of LPP directly inhibit lymphocytes but generally cannot induce clinical remission [3]. Therefore, there remains a critical unmet therapeutic need for an alternative topical product to treat LPP.

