### **3 Study Design**

#### **3.1 General Description**

This is a single arm, open label, exploratory study to evaluate the efficacy of Valchlor in the treatment of LPP. Subjects will be screened by the Department of Dermatology at the Mayo Clinic in Florida outpatient clinic and interested qualified subjects will be consented and offered participation. This study is designed to establish feasibility and proof of concept and will not include randomization or crossover components.

Patients with biopsy proven LPP who have failed one prior topical or systemic therapy with evidence of active disease will be eligible to participate. The presence of active disease will be based on a baseline clinical exam showing perifollicular erythema with scaling. Patients with predominance of end stage scarring hair loss but without significant active erythema will be excluded. Involvement restricted to the frontal scalp is a recognized clinical variant of LPP and is known as frontal fibrosing alopecia (FAA). As the histological features of LPP and FAA are identical, patients with FAA subtype of LPP would also be eligible to participate in the study.

Eligible participants using high-potency topical corticosteroids, intralesional corticosteroids, or oral hydroxychloroquine may enroll but will be required to discontinue use during the study period.

All study participants will apply Valchlor 0.016% gel to involved areas at night, beginning with three times a week (Mondays, Wednesdays and Fridays) and increasing to daily application after one month, if well tolerated. Patients will be instructed to first part the hair away from involved area as needed, limit application to areas with alopecia and erythema, apply 30 minutes after showering or washing, and allow treated areas to dry for 5 to 10 minutes before covering with clothing or going to bed. Participants will be instructed to wash their hands with soap and water after applying Valchlor. Caregivers who assist in application will be instructed to wear disposable nitrile gloves when applying Valchlor and dispose with the household trash. Patients will be instructed to store Valchlor in the refrigerator away from foods at 36°F - 46°F and apply within 30 minutes after removing from refrigeration.

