### 3.4 Primary Study Endpoints

The primary outcome measure of efficacy will be the percent reduction of baseline Lichen Planopilaris Activity Index (LLPAI) score after 6 months of treatment defined as follows.

- Complete response: LLPAI reduction greater than 85% from baseline score.
- Partial response: LLPAI reduction of between 25-85% from baseline score.
- Non-response: LLPAI reduction of less than 25% from baseline score.

The Lichen Planopilaris Activity Index (LPPAI) is a standardized validated quantitative measure of disease activity [12]. LPPAI score (0-10) is calculated as follows: (pruritus + pain + burning)/3 + (scalp erythema + perifollicular erythema + perifollicular scale)/3 + 2.5 (pull test) + 1.5 (spreading/2). Symptoms and signs are graded on a 4-point scale with 0 = absent, 1 = mild, 2 = moderate, and 3 =severe. Clinical progression and a positive hair pull test are graded 1=yes; 0=no.

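### Topical corticosteroid is permitted on the treated scalp with no cut-off before the Week 24 LPPAI, and users are scored like non-users, so their response cannot be attributed to Valchlor alone

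*Combined protocol and SAP*

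**What the plan says.** Two places allow topical corticosteroid on treated skin during the study. Section 5.6 (Prior and Concomitant Therapy) says "Mild irritant reactions at site application may be treated with class IV topical corticosteroids in a gel vehicle the morning following nightly application", to be used "on an as needed basis". Section 8.1, under Adverse Event, says a participant with signs of allergic contact dermatitis will be "offered treatment using a medium-potency topical corticosteroid to involved areas in the AM, with resumption of Valchlor application in the PM". Neither gives an end date, a maximum amount or a steroid-free interval before an LPPAI assessment.

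Other steroids must stop. Section 5.6 says "Eligible participants using high-potency topical corticosteroids, intralesional corticosteroids, or oral hydroxychloroquine may enroll but will be required to discontinue use", and Section 3.1 gives the same rule ("will be required to discontinue use during the study period"). Low- and medium-potency topical products are not on that list.

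Section 3.4 defines the primary outcome as "the percent reduction of baseline Lichen Planopilaris Activity Index (LLPAI) score after 6 months of treatment", with response classes set by that percentage alone. Sections 7.2 and 7.3 contain no rule for steroid users; the only sensitivity analysis planned removes participants who withdrew. Section 5.3 confirms that there is no placebo arm.

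Some capture exists. Current medications are reviewed at Weeks 12 and 24 (Section 6), adverse events are sought at each contact (Section 8.2), and the adverse event form asks whether an intervention was needed (Section 8.3.1). No analysis uses this information.

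**The concern.** Section 1.1 names topical corticosteroids among the conventional agents "used in the treatment of LPP directly inhibit lymphocytes", although the same sentence says these agents generally do not bring about remission. Section 1.6, item 5, says that mechlorethamine dermatitis shows as redness, itch and scale and responds well to topical steroid. Pruritus is an LPPAI item, and the LPPAI sign term is ("scalp erythema + perifollicular erythema + perifollicular scale)/3". The steroid may therefore act on the disease and on a drug reaction that looks like the disease, and both are read through the same items. PGA is graded largely on erythema, so it offers no independent check.

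At stake is what the response rate means. Section 7.1 wants an early efficacy estimate for planning a larger study, and Section 7.2 intends a comparison with published hydroxychloroquine and mycophenolate results. Both uses need to know whether the figure describes Valchlor or Valchlor with steroid.

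**Working it through.** **Inputs from Section 3.4.** LPPAI = (pruritus + pain + burning)/3 + (three scalp signs)/3 + 2.5 × pull test + 1.5 × (spreading/2). Symptoms and signs are graded 0–3; pull test and spreading 0 or 1. Partial response starts at a 25% reduction; complete response needs more than 85%.

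**Assumption.** The documents give no steroid effect on LPPAI. Assume a one-grade fall below baseline in pruritus and the three signs, with nothing else changing.

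**Fall in score.** 1/3 + 3/3 = 1.33 points.

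**Baselines at which this alone changes the class.**
- Partial response: 1.33/0.25 = 5.33 or below.
- Complete response: 1.33/0.85 = about 1.57; the baseline must be below this.
- Three signs only (1.0 point), partial response: 1.0/0.25 = 4.0 or below.

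**Worked profiles, one-grade fall in the four items.**

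| Baseline profile | LPPAI before | LPPAI after | Reduction | Class |
|---|---|---|---|---|
| All six items mild, pull test and spreading negative | 2.00 | 0.67 | 67% | Partial |
| All moderate, both negative | 4.00 | 2.67 | 33% | Partial |
| All moderate, spreading positive | 4.75 | 3.42 | 28% | Partial |
| All severe, both negative | 6.00 | 4.67 | 22% | Non-response |
| All moderate, both positive | 7.25 | 5.92 | 18% | Non-response |
| All severe, both positive | 9.25 | 7.92 | 14% | Non-response |

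A two-grade fall from 7.25 gives 4.58, a 37% reduction and a partial response.

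**Complete response.** With only the four items present, all mild, the score goes from 1.33 to 0. No minimum LPPAI is required at entry, so this profile is possible, but it is an extreme case.

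**The opposite direction.** Take a baseline of 4.00 and suppose Valchlor alone brings LPP to 2.67, a 33% reduction. If dermatitis that steroid has not fully controlled adds one grade to the same four items, the Week 24 score is 2.67 + 1.33 = 4.00: a 0% reduction and non-response. The same 1.33 points can thus create a responder or hide one.

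**Effect on the rate.** With 20 participants assessed, each changed classification moves the rate by 1/20 = 5 percentage points. The documents do not say how many will use steroid.

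**The case against.** A reader might infer that the plan inflates the response rate. The documents do not show that. The steroid is allowed only for reactions to Valchlor, and those reactions raise LPPAI items. Some of its effect may simply undo a drug-induced rise, and incomplete control would lower response. The one-grade fall is also purely assumed. Section 1.1 limits what conventional agents achieve, and Section 3.1 requires one prior topical or systemic failure, so some participants may already have failed topical steroid. This stands: the direction is open.

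A reader might also infer that complete responses are in doubt. Under the one-grade assumption that needs a baseline below about 1.57, so the issue is mainly partial response. Nor is the steroid a hidden comparator; it is concomitant medication.

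The potency wording is unsettled. Section 4.4.1 lists as a reason for discontinuing dermatitis that low-potency steroid cannot control, and Section 8.5 uses the same potency. Section 8.1 keeps a participant on medium-potency steroid in the study, and Section 5.6 names class IV. If Section 4.4.1 governs, participants needing the Section 8.1 regimen may leave before Week 24 and have no final LPPAI. This too stands, and it makes the number of affected participants harder to foresee.

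Finally, response to Valchlor with its permitted side-effect management is a legitimate target for a pilot, and a split of a few users across three classes will be imprecise. Both are fair. But the plan does not state that target: Section 2 speaks of Valchlor alone, and existing records of intervention feed no analysis.

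**Conclusion.** The point holds as one of attribution. As written, the Week 24 response in steroid users reflects Valchlor plus steroid, and the plan has no means of separating them or showing how much of the rate depends on users. Neither an upward bias nor any particular size of bias is established. The thresholds above follow exactly from the Section 3.4 formula but rest on an assumed one-grade fall. The 5 points per participant is arithmetic on 20 assessed participants; it bounds the effect only once the number of users is known, and reaches that bound only if every user's class turns on the steroid. This should be addressed, because the estimate is meant to inform a larger study and a comparison with published treatments. It is not a reason to change the permitted treatment.

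**What to change.** Leave clinical management unchanged.

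1. Extend the Week 12 and 24 medication review and the adverse event intervention field (Sections 6 and 8.3.1) to record scalp steroid product, start and stop dates, and use within a window fixed in advance before the Week 24 LPPAI, for example 28 days.
2. In Section 7.2, report the three response classes by use in that window. Add one prespecified supportive summary in which users are not counted as responders to Valchlor alone.
3. Describe the headline result as response to Valchlor with permitted topical steroid.
4. Reconcile the steroid potency wording in Sections 4.4.1, 5.6, 8.1 and 8.5, so that recorded use and withdrawals can be interpreted.

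The cost is one CRF line and one table with small cells. The supportive rate may be lower than the headline rate. It is a conservative summary, not a corrected estimate, because some users may have responded to Valchlor.
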